Trial Protocol

Version No:2

Version Date: 9/5/2020

Article information: <https://dx.doi.org/10.21037/gc-24-190>

The Use of Prophylactic Infusion of Calcium Gluconate Compared to Placebo in Reducing the Rate of Early Hypocalcaemia After Total Thyroidectomy: A Double- Blinded, Randomized Controlled Trial

Study Duration: 1/6/2020—13/5/2022

TABLE OF CONTENTS

Title Page	1
Table of Contents	2-3
List of Abbreviations	4
Introduction	5
Literature Review	6-8
Objective and Hypothesis	9
Study Endpoint	9
Methodology:	10-14
Current Protocol in UMMC	
Study Type and Design	
Target Population	
Sample Size	
Inclusion Criteria	
Exclusion Criteria	
Withdrawal Criteria	
Study Duration and Timeline	
Data Collection Tools and Techniques	
Data Analysis	
Risk and Benefit to Study Participants	
Flow Chart	15
Ethics of Study	16
Informed Consent	16
Privacy and Confidentiality	16
Conflict of Interest	16

Costing	16
Gantt Chart	17
References	18-19
Appendices	20-22
Appendix 1	
Appendix 2	
Appendix 3	

List of Abbreviations

b.d.- twice a day

ECS- endocrine surgery unit

EMR- electronic medical record

FDA- Food and Drug Administration

MREC- Medical Research Ethics Committee

PTH- parathyroid hormone

i-PTH- serum parathyroid hormone

o.d.- once a day

q.i.d.- four times a day

t.d.s.- three times a day

UMMC- University Malaya Medical Centre

WHO- World Health Organization

Introduction

Total thyroidectomy is a commonly performed procedure nowadays. It is the treatment option for thyroid malignancies and also for benign disease such as symptomatic multinodular goitre². Hypocalcaemia is one of the most common complications associated with total thyroidectomy and it has been reported to occur in 13%- 49% of cases in a meta-analysis, causing transient and permanent hypocalcaemia⁵.

In the UMMC Endocrine Surgery Unit (ECS), the incidence rate of post total thyroidectomy symptomatic hypocalcaemia within 48 hours after surgery in 2018 and 2019 were 40% and 23% respectively. The group of patients that required rescue doses of intravenous calcium gluconate infusion within 48 hours after surgery was 40% and 33% in 2018 and 2019 respectively. None of the patients that received intravenous calcium gluconate experienced any adverse effects in 2018 and 2019.

Post-thyroidectomy hypocalcaemia arises due to either parathyroid removal, parathyroid devascularization or gland damage⁴. Even with experienced surgeons and preservation of the parathyroid glands at the time of surgery, symptomatic hypocalcaemia can still occur². General consensus suggests that only one half of a normal parathyroid gland needs to be preserved to yield adequate parathyroid hormone.

Hypocalcaemia causes symptoms such as paraesthesia, muscle spasms, nervousness and anxiety. Classical signs would be Chvostek's and Trousseau's signs. Persistent symptomatic hypocalcaemia will lead to prolonged hospital stay, with increased patient cost and patient dissatisfaction.

There has been multiple reports that prophylactic administration of oral calcium supplement and vitamin D post-surgery is effective in reducing the rate of post-operative hypocalcaemia. However, there is a paucity of literature regarding the role of prophylactic infusion of calcium prior, during or after surgery in reducing the risk of developing post-operative hypocalcaemic symptoms.

The main aim of this study is to establish whether the administration of prophylactic infusion of calcium gluconate as compared to placebo reduces the rate of post-total thyroidectomy hypocalcaemia in the first 48 hours after surgery.

Literature Review

According to the 'Firth National Audit Report 2017' of The British Endocrine and Thyroid Surgeons (BAETS), the overall rate of early hypocalcaemia is 23.6%, compared to 27.4% in the 2012 report and 29.6% in the 2009 report¹. These figures probably represent an under-estimate of the true rate of early hypoparathyroidism as some patients would have received prophylactic calcium supplements in order to prevent post-operative hypocalcaemia. In the BAETS audit, the rate of early hypocalcaemia was as high as 30.4% in total thyroidectomy plus central node dissection group¹. The standard post-operative stay in that audit was a two-night stay and currently, in the UK, they are moving towards the trend of a one-night stay depending on the serum calcium level.

Several risk factors have been identified to cause temporary hypocalcaemia post-total thyroidectomy and common causes include accidental parathyroid removal and disruption of blood supply to the parathyroid glands. The treatment of symptomatic hypocalcaemia is intravenous infusion of calcium gluconate. There is limited data on the prophylactic use of intravenous calcium gluconate in preventing or reducing the rate of hypocalcaemia. A prospective cohort study by Urono, *et al* in 2006 showed that a significantly lower rate of post-total thyroidectomy hypocalcaemia was achieved by giving prophylactic infusion of calcium solution within 3-8 hours after surgery. The serum calcium level for the intervention group on the first post-operative day was 7.91 +/- 0.49 mg/dL while in the control group it was 7.65 +/- 0.54 mg/dL. There was no difference in the serum intact parathyroid hormone (i-PTH) level in both groups on the first post-operative day. This was the first prospective study that evaluated the role of prophylactic calcium infusion in reducing the rate of hypocalcaemia after total thyroidectomy².

Hafez, *et al* in the year 2014 found that in a randomized controlled trial involving 40 patients, prophylactic intravenous infusion of calcium gluconate during total thyroidectomy was effective in minimizing the risk for post-operative symptomatic hypocalcaemia³. These are the research currently available on the role of prophylactic intravenous calcium gluconate infusion after total thyroidectomy. Multiple factors can influence the rate of post-operative hypocalcaemia including patient characteristics or surgical technique. Rio PD, *et al* reported that females are at double risk of developing hypocalcaemia as compared to the male gender. Apart from that, the total thyroidectomy group have higher rates of hypocalcaemia as compared to the sub-total thyroidectomy group⁴. Total thyroidectomy plus central nodes dissection will increase the rate of post-operative hypocalcaemia even further as compared to total thyroidectomy alone (44% vs 14.3% of laboratory proven hypocalcaemia)⁷.

A meta-analysis by Xing TF, *et al* involving 10 randomized controlled trials suggested that routine post-operative calcium and vitamin D supplementation significantly reduced the rate of hypocalcaemia and the demand for intravenous calcium supplementation as compared to either no treatment or calcium alone^{5,12}. While there is evidence regarding the role of post-operative supplementation, there is little

literature reporting on the role of routine pre- and post-total thyroidectomy calcium and vitamin D supplementation in preventing post-operative hypocalcaemia. Routine pre- and post-total thyroidectomy calcium and vitamin D supplementation have been shown to reduce the rate of post-operative hypocalcaemia and length of hospital stay^{6,7}.

Interestingly, there was a randomized controlled trial performed by Besic, *et al* who studied whether magnesium infusion prior to total thyroidectomy will influence the onset of transient hypocalcaemia. This is as normomagnesaemia is needed for the normal secretion of parathyroid hormone. However, no statistical difference was identified between the intervention and control groups^{9,12}. It is essential to measure serum magnesium in any patient who is hypocalcaemic, as the correction of hypomagnesaemia must occur to overcome parathyroid hormone (PTH) resistance before serum calcium can be normalised with calcium supplementation¹⁴.

Pre-operative parathyroid hormone level can help to predict and anticipate post-operative hypocalcaemia. If the pre-operative PTH is less than 4.7pmol/L, the risk of developing transient hypoparathyroidism is 2.4 times higher than the normal population and thus there is a higher risk of developing post-operative hypocalcaemia¹⁰. Pre-operative calcium levels can also help to predict post-operative hypocalcaemia. A retrospective study by Amir, *et al* found that corrected pre-operative serum calcium levels of less than 2.27 mmol/L was associated with a 63% chance of developing post-thyroidectomy hypocalcaemia whereas those with calcium levels above 2.27 mmol/L have a 24% chance of developing hypocalcaemia¹¹.

Luo Han, *et al* performed a retrospective study of protocols for the post-thyroidectomy management of patients who underwent thyroidectomy between 2013 and 2015 in West China Hospital¹⁴. All patients were given routine 2-days of intravenous calcium infusion, 2g on the day of surgery and 4g on post-operative day 1. All patients were also prescribed with calcium carbonate 600mg t.d.s or q.i.d. on post-operative day 1. Extra calcitriol 0.25mcg b.d. was added into the therapeutic plan on a case-by-case basis. The patients were usually discharged on the third day after surgery depending on their serum calcium levels and the relative decrease in percentage between pre-operative i-PTH and postoperative i-PTH level (the cut-off percentage used was 70% decrease in i-PTH level). On the basis of their findings in this study, routine 2-day intravenous infusion of calcium with or without oral supplement plus extra supplement of calcitriol according to the relative decrease percentage and absolute value of post-operative PTH was an effective protocol that could identify patients needing longer hospitalization¹⁴.

Hypocalcaemia can present either as an asymptomatic laboratory finding or as a severe, life-threatening condition¹⁵. The ability to distinguish acute from chronic hypocalcaemia and asymptomatic from severely symptomatic hypocalcaemia is essential to determine the appropriate therapy. In the setting of

acute hypocalcaemia, rapid treatment may be necessary. In contrast, chronic hypocalcaemia may be well tolerated, but treatment is necessary to prevent long-term complications. Post total thyroidectomy hypocalcaemia is one of the causes of acute hypocalcaemia. The hallmark of acute hypocalcaemia is neuromuscular irritability. Patients often complain of numbness and tingling in their fingertips, toes, and the perioral region. Paraesthesia of the extremities may occur, along with fatigue. Muscle cramps can be very painful and progress to carpal spasm or tetany. In extreme cases of hypocalcaemia, bronchospasm and laryngospasm with stridor may occur. All these symptoms can be corrected by calcium replacement either in the oral or intravenous form depending on the clinical picture.

Clinically, neuromuscular irritability can be demonstrated by eliciting Chvostek's or Trousseau's signs. Chvostek's sign is elicited by tapping the skin over the facial nerve anterior to the external auditory meatus. Ipsilateral contraction of the facial muscles occurs in individuals with hypocalcaemia. It has to be noted that Chvostek's sign is also present in 10% of normal individuals¹⁵. Trousseau's sign is elicited by inflation of a blood pressure cuff to 20 mm Hg above the patient's systolic blood pressure for 3-5 minutes. Carpal spasm presents as flexion of the wrist and of the metacarpal phalangeal joints, extension of the interphalangeal joints, and abduction of the thumb. Cardiac manifestations such as prolonged QT interval, abnormal T wave and cardiac arrhythmias could be one of the features of acute hypocalcaemia. Thus, by classifying hypocalcaemia into mild or severe, depending on the clinical symptoms and biochemical results can be useful to direct treatment strategy (**Appendix 3**).

Calcium gluconate is the intravenous calcium salt of choice to correct hypocalcaemia as calcium chloride often causes local irritation. In most hospital settings, only calcium gluconate is readily available. Calcium gluconate contains 90 mg of elemental calcium per 10 mL ampoule, and usually 1 to 2 ampoules (180 mg of elemental calcium) diluted in 50 to 100 mL of 5% dextrose is infused over 10 minutes. This can be repeated until the patient's symptoms have resolved. With persistent hypocalcaemia, administration of a calcium gluconate infusion over a longer period of time may be necessary. Infusion rates of 0.5-2.0 mg/kg/hour are recommended¹⁵.

The most common adverse effects of intravenous calcium infusion are hypertension, nausea, vomiting, and flushing. Bradycardia and heart block may occur in rare cases. Patients receiving intravenous calcium should be placed on cardiac monitoring and administration should be discontinued if bradycardia ensues. Patients may complain of tingling sensation, a sense of oppression or heat wave and a calcium or chalky taste following administration of intravenous calcium gluconate. As extravasated calcium may cause severe tissue irritation and necrosis, it should be given through a well-functioning intravenous catheter^{16,17}.

Objectives

Primary Objectives

- To determine whether prophylactic infusion of calcium gluconate reduces the rate of early hypocalcaemia after total thyroidectomy as compared to placebo treatment

Secondary Objectives

- To determine whether prophylactic infusion of calcium gluconate reduces the length of hospital stay as compared to placebo group

Study Endpoint

- The level of corrected calcium in the first 48 hours after total thyroidectomy between intervention and control group

Hypothesis

- Null hypothesis: prophylactic infusion of calcium gluconate does not reduce post-total thyroidectomy hypocalcaemia and length of hospital stay as compared to placebo group
- Alternative hypothesis: Prophylactic infusion of calcium gluconate reduces the rate of post-total thyroidectomy hypocalcaemia in the first 48 hours and shorten the length of hospital stay as compared to placebo group

Methodology

Current Protocol in UMMC

All patients admitted or scheduled for total thyroidectomy in UMMC will have their baseline serum calcium and i-PTH levels checked one day before surgery. Subsequently, all patients will have their serum calcium levels checked at the 6-hour, 12-hour, 24-hour, 36-hour and 48-hour mark post-surgery. The i-PTH level will be tested at the 12-hour post-surgery mark together with the serum calcium level. Oral calcium supplements 2g a day (Calcium Carbonate 1g b.d.) and Rocaltrol 0.25mcg o.d. will be started once the patients are able to tolerate orally. If a patient experiences symptoms of hypocalcaemia and the serum calcium level is less than 2.0mmol/L, the patient will be administered a rescue dose of intravenous calcium gluconate (3g of calcium gluconate in 50mls of normal saline) over 4 hours duration. However, if a patient experiences hypocalcaemia symptoms and the serum calcium level is more than 2.0mmol/L, the patient will be continued on oral supplements at an increased dosage (3-4g of calcium carbonate a day). The usual hospital stay for a total thyroidectomy patient is 48 hours post-surgery. If a patient is asymptomatic and the serum calcium level is normal at 48-hours post-surgery, the patient can be discharged with an appointment at the outpatient clinic in two weeks time.

Study Type and Design

This is a single centre, double blinded and prospective randomized controlled trial which will be conducted in University Malaya Medical Centre (UMMC), Endocrine Surgery Unit. The duration of the study will be from June 2020 until May 2022 (2 years duration).

Patient will be recruited from the endocrine surgery outpatient clinic and in-patient referrals for total thyroidectomy. There are several inclusion and exclusion criteria for recruitment into this study. After fulfilling the inclusion criteria, patients will be required to give consent and agree to participate in this study after explanation by the clinician and investigator in charge. Participants will be randomized into an intervention group (Group A) and a control group (Group B) with the ratio of 1:1 during admission for surgery (**Appendix 2**). The method of randomization utilised will be random randomization. Both the surgeon and patient will not be aware of the randomization arm of any particular patient. Only the primary investigator and assistants will be aware of the randomization of a patient. Before surgery, baseline serum calcium, magnesium and i-PTH will be obtained. If intra-operatively, all 4 parathyroid glands are accidentally removed during the total thyroidectomy, these patients will be excluded from the study as this will definitely affect their serum calcium levels post-surgery.

After total thyroidectomy, the intervention group will receive a calcium gluconate infusion over one hour (1g of intravenous calcium gluconate, diluted in 100mls of normal saline) within 4 hours after skin closure. On the other hand, the control group will receive a saline infusion (100 ml of normal saline) infused over one hour within 4 hours of skin closure. Both groups will be put on cardiac monitoring

during the administration of the intravenous infusion. The dosing, dilution and infusion rate for the calcium gluconate are within the safety limits as recommended by FDA and WHO model formularies.

Post-total thyroidectomy, both groups of patients will receive the same regime of oral calcium carbonate 1g t.d.s. and oral Rocaltrol 0.25mcg o.d. as per current protocol in the endocrine surgery unit. Serum calcium levels will be obtained at the 6-hour, 12-hour, 36-hour, 48-hour mark post-surgery. The blood samples collected will be sent to the biochemical laboratory of UMMC.

During blood taking and review, the patient will be assessed for symptoms of hypocalcaemia such as perioral numbness, spasm, etc. During assessment, if there are clinically suggestive symptoms of hypocalcaemia, the symptoms will be classified into mild or severe symptoms (**Appendix 1**). If a patient exhibited signs of mild hypocalcaemia like perioral numbness, limbs numbness and positive Chvostek's sign, then immediate biochemical investigations including corrected serum calcium level will be performed and the results traced. If the results show serum hypocalcaemia (less than 2.0mmol/L) and patient is experiencing mild hypocalcaemic symptoms, a rescue dose of intravenous calcium gluconate (3g of intravenous calcium gluconate infusion over 4 hours) will be given as per current unit protocol. After completion of the rescue dose of calcium infusion, the serum calcium level will be repeated and further action will be taken based on the post-correction serum calcium level.

However, if the patient developed severe hypocalcaemia symptoms such as carpo-pedal spasm, bronchospasm/laryngospasm or cardiac manifestation, then an immediate biochemical investigation (corrected serum calcium level) will be obtained and an immediate rescue dose of intravenous calcium gluconate will be administered to the patient before the result are available. According to current unit protocol, if a patient developed severe hypocalcaemia symptoms, an immediate intravenous calcium slow bolus (1g of calcium gluconate) will be given over 20 minutes. This will be followed by intravenous calcium infusion (3g of intravenous calcium gluconate infusion over 4 hours) after biochemical confirmation of hypocalcaemia. After completion of the slow calcium bolus and calcium infusion, serum calcium levels will be repeated and further action will be determined based on the post-correction serum calcium level. The management of hypocalcaemic patients can be referred to **Appendix 3**. Both groups of patients will be followed-up until 48 hour post-operation. In the event of an emergency and there is a need to break the code, the clinician in charge of the patient will contact the principal investigator immediately to facilitate the rescue process.

In the endocrine surgery unit, the current practice is that all patients who had total thyroidectomy performed will be kept as an in-patient routinely for at least 48 hours so that their serum calcium levels can be monitored at the intervals mentioned above (6-hour, 12-hour, 24-hour, 36-hour & 48-hour). Therefore, this study will not incur an additional stay or prolonged admission.

Target Population

The target population is from the endocrine surgery clinic and UMMC ward. Target population consists of all patients scheduled for total thyroidectomy during the period of 1st June 2020 to 31st May 2022.

Sample Size

A pilot study will be conducted after obtaining approval from MREC (Medical Research Ethics Committee) UMMC. 10 patients will be recruited for the pilot study and randomized into 5 patients each arm. Sample size calculation will then be derived from the mean and standard deviation obtained from the pilot study.

Inclusion Criteria

- Age between 18-80 years old
- Scheduled for total thyroidectomy in UMMC

Exclusion Criteria

- Their age outside the range of 18-80
- Have parathyroid disorders or end stage renal failure
- On calcium or vitamin D supplements prior to surgery
- Have deranged calcium homeostasis pre-operatively (outside the normal range of 2.2-2.6 mmol/L)
- Scheduled for total thyroidectomy plus lymph node dissection

Withdrawal Criteria

Subjects can choose to withdraw at any time and withdrawn subjects will not be replaced.

Study Duration and Time-line (refer to Gantt Chart)

The total research period is from October 2019 till February 2023. The first two months will be spent on literature review of the relevant papers and the next two months will be on preparation of the research proposal. Subsequently, the research proposal will be submitted to MREC for approval.

After the proposal is approved by MREC, data collection will tentatively start from June 2020 till May 2022. Subsequently, data analysis will start from June 2022 till October 2022. Another two months will be spent on the final report writing and finally thesis presentation and submission on January to February 2023. (please refer to the Gantt chart)

Data Collection Tools and Techniques

As this is a prospective randomized controlled trial, relevant participants information and blood investigations will be recorded and documented in the Electronic Medical Record (EMR). These data will then be transcribed into SPSS for analysis.

Data Analysis

Data recorded will be analysed using SPSS Statistics Version 25. Continuous data will be expressed as Mean \pm standard deviation unless otherwise stated. Paired T- test was used for comparison of paired samples. The students's T- test was used for comparison of continuous variables between different groups. Chi-square test will be used for categorical data analysis. A value of $P < 0.05$ will be considered statistically significant. The data collected will be analysed using an per-protocol analysis.

[figure not shown]
Risk and Benefit to Study Participants

The dose and infusion rate of calcium used in this study is within the safety limits proposed by the World Health Organization (WHO). The adverse effects of calcium infusion are rare and may range from mild to severe. Common adverse effects including nausea, vomiting, hypertension, flushing and local inflammation over the infusion site. Severe adverse effects such as heart block and slow heart rate may occur but are extremely rare with this regime and dosage of calcium infusion. All study participants will be placed on cardiac monitoring and administration will be discontinued if adverse effects supervene. None of the patients in the endocrine surgery unit, UMMC experienced

any adverse effect after receiving intravenous calcium gluconate in the year 2018 and 2019. Therefore, there is very minimal risk for subjects who choose to participate in this study.

In the other hand, this study does not present any direct benefit to the participants who involved in this study. However, information obtained from this study will help to formulate a better treatment protocol/plan to reduce and prevent incidences of hypocalcaemia after total thyroidectomy.

Flow Chart

Ethical Consideration of Study

This study will be conducted in compliance with ethical principles outlined in the Declaration of

Helsinki and Malaysian Good Clinical Practice Guideline.

Informed Consent

Eligible patients will be identified during clinic visits. Information regarding the study will be given and explained to them during clinic visit. They will be allowed to take the patient information sheet home and consult with their family members. Informed consent will be obtained when they are admitted for surgery.

Privacy and Confidentiality

Subject's names will be kept private and an identification number instead of patient identifiers will be used on subject data sheets. Strict confidentiality will be maintained. All identification labels will be anonymised in any future presentations or publications. All data will be entered into a computer that is password protected. On completion of study, data in the computer will be copied to a thumb-drive/USB drive and the data in the computer erased. Thumb-drive/USB drive and any hardcopy data will be stored in a locked office of the investigator in the Department of Surgery and securely disposed after 7 years on conclusion of the study.

Conflict of Interest

The investigators declare that they have no conflict of interest. The expense for the cost of the investigational product will be borne by the principal investigator.

Gantt Chart

	OCT –NOV 2019	DEC 2019- JAN 2020	FEB-APRIL 2020	JUNE 2020- MAY 2022	JUNE-OCT 2022	NOV-DEC 2022	JAN-FEB 2023
LITERATURE REVIEW	■						
THESIS PROPOSAL		■					
ETHICS APPROVAL			■				
DATA COLLECTION				■			
DATA ANALYSIS					■		
REPORT WRITING						■	
THESIS SUBMISSION							■

References

2. Uruno T., et al., A prophylactic infusion of calcium solution reduces the risk of symptomatic hypocalcemia in patients after total thyroidectomy. *World J Surg*, 2006. 30(3): p. 304-8.
3. Hafez AT., et al., The role of intraoperative calcium injection for prevention of post-operative hypocalcaemia after total thyroidectomy. *Menoufia Medical Journal*, 2014. 27(4): p. 629-31.
4. Rio PD., et al., Postoperative hypocalcemia: analysis of factors influencing early hypocalcemia development following thyroid surgery. *BMC Surgery*, 2019. 18(1):25: p. 1-8.
5. Xing TF., et al., Role of oral calcium supplementation alone or with vitamin D in preventing post-thyroidectomy hypocalcaemia. *Medicine*, 2019. 98(8): p. 1-8.
6. Jaan S., et al., Usefulness of pre- and post-operative calcium and vitamin D supplementation in prevention of hypocalcemia after total thyroidectomy: A randomized controlled trial. *Indian Journal of Endocrinology and Metabolism*, 2017. 21(1): p. 51-5.

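### The objective and hypothesis concern the rate of early hypocalcaemia, but the only endpoint is a calcium level and the sample size rests on a mean and SD, so no rate endpoint is defined or sized.

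*Protocol*

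**What the plan says.** The title speaks of reducing the rate of early hypocalcaemia. The primary objective is "To determine whether prophylactic infusion of calcium gluconate reduces the rate of early hypocalcaemia after total thyroidectomy as compared to placebo treatment". The alternative hypothesis is that "Prophylactic infusion of calcium gluconate reduces the rate of post-total thyroidectomy hypocalcaemia in the first 48 hours", and it adds a shorter hospital stay to the same statement.

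The Study Endpoint section has one entry: "The level of corrected calcium in the first 48 hours after total thyroidectomy between intervention and control group". It fixes no time point, summary measure or event.

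Under Sample Size, "10 patients will be recruited for the pilot study and randomized into 5 patients each arm", and "Sample size calculation will then be derived from the mean and standard deviation obtained from the pilot study". The variable is not named. Calcium is inferred because it is the sole listed endpoint; length of stay is the other continuous outcome in the protocol. No N, power or effect size is given.

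Data Analysis names Student's t-test for continuous variables and chi-square for categorical data, without linking either to an endpoint.

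Two calcium values appear. In the rescue rule under Study Type and Design: "If the results show serum hypocalcaemia (less than 2.0mmol/L". Under Exclusion Criteria, for pre-operative calcium: "outside the normal range of 2.2-2.6 mmol/L". Neither is attached to the objective.

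For patients who have mild symptoms and a value below 2.0 mmol/L, "a rescue dose of intravenous calcium gluconate (3g of intravenous calcium gluconate infusion over 4 hours) will be given as per current unit protocol". This falls within the 48-hour follow-up. The Introduction reports that 40% (2018) and 33% (2019) of the unit's patients needed rescue infusions within 48 hours.

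**The concern.** A rate and a mean are different estimands. Mean calcium can rise because patients already in the normal range go higher, with no change in the number who become hypocalcaemic. Conversely, the number of hypocalcaemic patients can fall with little movement in the mean. A positive t-test on the level would therefore not support the conclusion the trial has set itself.

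Three consequences follow.

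- The event behind the word rate is not fixed in the text shown. It could be biochemical, symptomatic or both, and it could be chosen after the data are seen.
- A sample size taken from a mean and SD says nothing about power for a proportion.
- Calcium measured after rescue reflects the rescue as well as the study infusion. If prophylaxis works, controls receive rescue more often, and their later values are raised more often.

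**Working it through.** **The plan's own figure.** There is none to reproduce, because N is deferred to the pilot. Everything below is illustration, with two-sided alpha 0.05, 1:1 allocation and 80% power. The sidedness and the 80% are assumptions.

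**1. Sizing on the mean.** The inputs are the day-1 values of the prospective cohort in the Literature Review: 7.91 (SD 0.49) and 7.65 (SD 0.54) mg/dL.

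- Pooled SD = √[(0.49² + 0.54²)/2] = √0.26585 = 0.516 mg/dL.
- Standardised difference = 0.26/0.516 = 0.504.
- n per arm = 2(1.960 + 0.842)²/0.504² = 2 × 7.849/0.2543 = 61.7, so 62, or about 63 with a small allowance for the t-distribution.

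**2. The same data expressed as a rate.** Assume normal distributions, with 2.0 mmol/L = 2.0 × 4.008 = 8.016 mg/dL.

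- Control: (8.016 − 7.65)/0.54 = 0.678, so 75.1% lie below.
- Infusion: (8.016 − 7.91)/0.49 = 0.216, so 58.6% lie below.
- Power = Φ{[|p₁ − p₂| − 1.96√(2p̄(1 − p̄)/n)] / √[(p₁(1 − p₁) + p₂(1 − p₂))/n]}, where p̄ is the average of the two proportions.
- At n = 62 or 63 this gives 50%.

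**3. The unit's own rates.** The Introduction gives symptomatic hypocalcaemia of 40% and 23%, and rescue of 40% and 33%. A halving is assumed, and the same power formula is used.

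| Control | Infusion | Power, 62 per arm | Power, 63 per arm | n per arm for 80% |
|---|---|---|---|---|
| 23% | 11.5% | 39% | 40% | 169 |
| 33% | 16.5% | 57% | 58% | 107 |
| 40% | 20% | 68% | 69% | 82 |

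**4. Rescue.** If rescue raises later calcium by r, and proportions q_C (control) and q_I (infusion) are rescued, the difference in later means shrinks by r(q_C − q_I). The starting difference is 0.26/4.008 = 0.065 mmol/L. Both r and the rescue proportions by arm are assumed.

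| q_C and q_I | r = 0.1 mmol/L | r = 0.2 mmol/L |
|---|---|---|
| 36% and 18% | loss 0.018 (28%) | loss 0.036 (55%) |
| 15% and 7% | loss 0.008 (12%) | loss 0.016 (25%) |

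The direction holds whenever controls are rescued more often. The amount does not transfer: the 0.065 comes from a cohort whose control mean was 7.65/4.008 = 1.91 mmol/L, which need not match this unit's patients. Values before first rescue are untouched.

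**The case against.** **A rate can still be compared.** Calcium and symptoms are recorded repeatedly and a chi-square test is named. This stands. A reader might infer that the trial cannot test its own question, but the text supports only that no such endpoint is defined or sized.

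**The trial is not shown to be underpowered.** This also stands. The protocol gives no N and does not name the pilot variable, so the 62 to 63 per arm is an illustration. A larger effect would change the picture: if the rate fell to 0.33 of control, 85, 54 or 42 per arm would suffice at control rates of 23%, 33% or 40%, and 62 would be enough in the last two cases. The borrowed cohort also implies a 75% control share, far above the unit's symptomatic and rescue rates, although a biochemical rate could be higher than those. With 2.2 mmol/L as the cut-off, nearly all of that cohort would be events. The very low power that results reflects a ceiling in the borrowed values and is not used here.

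**The two calcium values need not conflict.** A reader might infer two rival definitions of hypocalcaemia. One is a pre-operative eligibility range and the other part of a rescue rule, so they serve different purposes. An event definition may also sit in the appendices, whose content is not visible. What stands is that neither value is tied to the objective in the visible text.

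**Post-rescue handling is unstated, not wrong.** A reader might infer that values after rescue are to be analysed as if untreated. The protocol does not say so, and that rule is commonly left to an analysis plan. The unit's rescue figures may also overstate what the trial will see, because planned lymph node dissection and removal of all four glands are excluded. Rescue is therefore a supporting reason for a binary endpoint and not a separate error.

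None of this removes the mismatch between objective, endpoint and sample-size basis. All three are protocol content and are stated here.

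**Conclusion.** The point holds and should be fixed before the sample size is set. The title, primary objective and alternative hypothesis concern a proportion; the sole endpoint and the sample-size method concern a mean. As written, the plan neither defines nor sizes a test of its stated question.

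The size is conditional. Under the cited cohort's figures and normality, a trial with 80% power on the mean has about 50% power for the share below 2.0 mmol/L. Under an assumed halving of the unit's rates it has about 40% to 69%. Later calcium values would tend to understate a true difference because of rescue, by an amount the documents do not determine.

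**What to change.** - Replace the Study Endpoint entry with one binary primary endpoint: the proportion of patients with hypocalcaemia up to 48 hours. Fix one threshold before unblinding and before outcomes are viewed by arm, and state whether symptoms are required. Below 2.0 mmol/L is one candidate, since the protocol already calls that serum hypocalcaemia. The threshold is for analysis only.
- Count patients given rescue intravenous calcium as events.
- Compare the arms as a risk difference with a 95% confidence interval.
- Base the sample size and stated power on two proportions, or state the power that the recruitable N gives.
- Keep corrected calcium level as a secondary endpoint, without treating post-rescue values as untreated.
- Test length of stay as a separate secondary hypothesis.

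The cost is protocol wording and a new calculation. Blood samples and symptom checks are already planned, and no rescue or treatment rule changes. The real downside is less power at a given N than a continuous endpoint: with the assumed halving, 82 to 169 per arm for 80% power.
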